## 2.1.4. Collaborative objective

The blood leftover from subjects included in the TrypSkin sub-study, conserved in a nucleic acids-protective buffer (estimated at approximately 2 to 5 mL including preservative buffer per subject per time-point), will be donated to the WHO Specimen Biobank for future research on new tools for HAT control. Agreement of the subjects will be obtained through the Informed Consent Form (ICF), refusal will not be an exclusion for the participation in the TrypSkin sub-study.

## 2.2. Study endpoints

#### 2.2.1. Primary endpoint

• Occurrence of treatment-emergent adverse events (TEAEs).

## 2.2.2. Secondary endpoint(s)

- Occurrence of adverse events (AEs) from ICF signature to the EoS
- Change from baseline in ECG parameters, biochemistry and haematology
- Blood concentration of acoziborole at Day 5 and Month 1
- ΔQTc measurements at Day 5
- Placebo-corrected change from baseline in ECG parameters (double delta [ΔΔ] heart rate [HR], ΔΔRR, ΔΔPR, ΔΔQRS, ΔΔQT and ΔΔQTc)
- Incidence of abnormal values and morphological findings in ECG at Day (D)5

## 2.2.3. Exploratory endpoint(s) (TrypSkin sub-study)

#### Primary exploratory endpoint:

• Occurrence of extravascular dermal *T.b. gambiense* at enrolment and at 4 months by TgSGP-PCR in skin.

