## 1.6. Rationale for current study

Although the treatment options have advanced with the recent approval of fexinidazole (an effective 10-day oral treatment), there are still gaps with regards to the 2030 Public Health objective of sustained HAT elimination.

Indeed, the standard g-HAT case definition implies the demonstration of the parasite in any body fluid via microscopy. However, there are factors such as low parasitaemia and the complexity and low sensitivity of parasitological methods that make such demonstration difficult. It is known that there are some "indirect" signs of g-HAT that could indicate the presence of the parasites. The most known indirect signs of g-HAT are biological (positive antibody response to either available serological card agglutination test for trypanosomiasis [CATT], rapid diagnostic tests [RDTs; 11], or molecular tests) and clinical. In some circumstances, it has been suggested (11) to consider individuals presenting "indirect" signs, but without confirmatory observation of parasites in biological fluids (considered as g-HAT "suspected" individuals), as cases "eligible" for treatment. Only under special conditions, "suspected" g-HAT patients have been treated (12, 13, 14) since the complexity and toxicity of previously available treatment options typically precluded systematic treatment of these "suspects" due to an individual negative risk-benefit ratio. However, it has been demonstrated that a variable proportion (mainly depending on the prevalence) of such "suspects" are confirmed cases and, therefore, remaining as potential reservoirs of the parasite and a source of new infections hindering the efforts to eliminate the disease (11).

Acoziborole, as an oral single-dose treatment envisioned for all stages of g-HAT, is expected to help boost elimination efforts.

Acoziborole has been studied in an open-label pivotal Phase II/III trial (DNDi-OXA-02-HAT) in the DRC and Guinea. Eighteen months follow-up visits (primary endpoint) were successfully completed in August 2020 and study results (Tables, Figures and Listings) were issued in April 2021.

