#### Secondary exploratory endpoints:

- Clinical parameters: occurrence of dermatitis and/or pruritus at baseline and M4.
- Diagnostic parameters: occurrence of IHC+, TBR- PCR+ and/or 18S-PCR+ in skin and blood at baseline and M4.
- Novel diagnostic parameters: occurrence of positive results by multiplex qPCRs, multiplex RT-qPCRs and SHERLOCK in blood and skin at baseline and M4.

- Occurrence of dermatitis, pruritus, IHC+, multiplex qPCRs+, multiplex RT-qPCRs+ and SHERLOCK+ in skin and blood at baseline and at M4.
- Occurrence comparisons between all diagnostic methods alone or in combination.

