## 8.4. Exploratory assessments

For subjects participating in the TrypSkin exploratory sub-study, the following samples will be taken at screening (baseline) and 4 months (EoS):

- 3 mL fresh blood (in nucleic acid-preservative buffer) and 5 DBS
- Two 2 mm-skin-punch biopsies on the right back shoulder under local anaesthesia

Samples will be shipped to specialised partner laboratories (Institut National de Recherche Biomédicale [INRB], Institut Pasteur Guinea and Institut Pasteur Paris and Institute of Tropical Medicine [ITM] Antwerp) for the following analyses:

1- Molecular detection of trypanosomes:

- Common automatised extraction of total nucleic acids (TNAs) from fresh blood, DBS and skin biopsies
- On TNAs from fresh blood and skin (main validated diagnostic methods):
  - For all samples: TBR-PCR and 18S-PCR (*T. brucei s.l.*)
  - For TBR-PCR+ and/or 18S-PCR+ samples: T.b. gambiense-specific TgSGP-PCR
- On TNAs from fresh blood, DBS and skin (additional methods to be tested):
  - o qPCR detection using at least 2 targets
  - Multiplex RT-qPCR detection using novel targets
  - CRISPR-derived approach (SHERLOCK)
- 2- Immuno-histochemical detection of dermal trypanosomes:
  - At least 2 automatised IHC on Formalin-Fixed Paraffin-Embedded (FFPE) skin sections for all subjects with *T. brucei*-specific staining (Anti-Invariable Surface Glycoprotein 65 [ISG65] and Anti-cross reacting determinant [CRD] and secondary polymer amplification
  - Automatised acquisition and double *in silico* blind reading, pictures annotation and archiving
- 3- Preliminary tests for the detection of trypanosomes by Raman spectroscopy:
  - For each subject at each time point, one DBS from the field and one FFPE slide generated for IHC at IP Paris will be scanned by Raman spectroscopy at the University of Glasgow in the context of an exploratory procedure based on the measurements of biophysical parameters associated to the presence of trypanosomes.

• The results will not be uploaded in the central data base as the final analyses will rely on machine learning approaches after the end of the study.

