#### Primary diagnostic parameter

A subject is considered positive to extravascular dermal *T.b. gambiense* if TgSGP-PCR test in skin is positive.

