5.3. Exploratory Objectives (Sub-study) Analysis

5.3.1. Exploratory Analysis

The primary set of subjects for exploratory efficacy analyses is the Safety set composed of subjects who participated in the TrypSkin sub-study. The primary exploratory objective is to establish whether acoziborole reduces the occurrence at 4 months of dermal trypanosomes in comparison with placebo. The exploratory efficacy will be evaluated using diagnostic and clinical endpoints. The primary diagnostic endpoint will be dermal trypanosome positive if TgSGP-PCR in skin is positive and the clinical endpoint will be the occurrence/presence of dermatitis and/or pruritus symptoms at 4 months. The occurrence rate of positive dermal trypanosome at 4 months based on the primary diagnostic parameters will be the primary measure of interest because the sample size is under control, and it corresponds to a measure of the level of potential transmission of reservoirs. The magnitude of the treatment effect will be the odds ratio of positive dermal trypanosomes. A Cochran Mantel Haenszel test using sites as strata will be used to compare acoziborole and placebo occurrence rate at 4 months of positive dermal trypanosome as well as occurrence of dermatitis and/or pruritus symptoms. In case of small proportions, the exact Cochran-Mantel-Haenszel (CMH) test will be performed. The Breslow-Day test of homogeneity of the odds ratio across sites will be performed to assess the generalizability of the treatment effect. If the test is significant, a forest plot will be provided to display the heterogeneity of the magnitude of treatment effect across sites and to detect sites explaining the heterogeneity.

As the odds ratio is not easy to interpret when the rate of positive subjects in the placebo group is not small ($P_0 > 0.05$), the odds ratio (OR) will be converted into the risk ratio (RR) using the following formula:

$$RR = \frac{P_1}{P_0} = \frac{OR}{(1 - P_0) + P_0 \times OR)}$$

where P_1 and P_0 are the estimated proportions of positive subjects in the acoziborole group and placebo group respectively. The excess rate $(P_1 - P_0)$ will also be estimated as a secondary measure of the magnitude of the treatment as well as the NTT (number of subjects needed to treat to get one less positive subject at 4 months in acoziborole group. The exploratory efficacy analysis results will be presented and individual data listing.

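### The TrypSkin primary endpoint calls any skin TgSGP-PCR positive extravascular, a location the assay cannot show, and the paired conventional blood PCR is not used to qualify it

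*Protocol*

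**What the plan says.** Protocol 2.2.3 defines the primary exploratory endpoint as extravascular dermal T.b. gambiense "at enrolment and at 4 months by TgSGP-PCR in skin". Protocol 10.8 (Primary diagnostic parameter) counts a subject as positive for it "if TgSGP-PCR test in skin is positive", with no condition on blood PCR or immunohistochemistry (IHC). SAP 1.2.2 keeps the word extravascular. SAP 5.3.1 applies the same test under a looser label: "The primary diagnostic endpoint will be dermal trypanosome positive if TgSGP-PCR in skin is positive".

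The sample is described in Protocol 8.4: "Two 2 mm-skin-punch biopsies on the right back shoulder under local anaesthesia". The PCR template comes from "Common automatised extraction of total nucleic acids (TNAs) from fresh blood, DBS and skin biopsies". The conventional cascade is listed under "On TNAs from fresh blood and skin (main validated diagnostic methods": TBR-PCR and 18S-PCR on every sample, then TgSGP-PCR on samples positive for either. Each sub-study subject therefore has a paired blood result at baseline and at Month 4.

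The secondary endpoints in Protocol 2.2.3 include "occurrence of IHC+, TBR- PCR+ and/or 18S-PCR+ in skin and blood at baseline and M4". TgSGP-PCR in blood is not named there. Protocol 4.1 requires negative parasitology at entry, and Protocol 1.6 refers to "low parasitaemia and the complexity and low sensitivity of parasitological methods that make such demonstration difficult".

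**The concern.** The sub-study asks whether the skin is a reservoir that blood examination misses (Protocol 1.6). A PCR on nucleic acids from a whole punch reports that parasite DNA was present, not which compartment it came from. A subject with parasites only in blood could be counted as an extravascular carrier.

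Two claims depend on the label. One is the baseline prevalence of extravascular dermal parasites. The other is the Month 4 comparison, read as elimination from the dermis (Protocol 2.1.3). A drug that cleared blood alone could lower skin PCR positivity to some degree and be credited with dermal clearance. The randomised comparison of skin PCR positivity would still be valid; its interpretation is what is open.

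**Working it through.** **1. The plan's own figures.** Protocol 10.1.1 assumes 20% prevalence and a 95% CI of ±3 points. n = z²p(1−p)/d² = 1.96² × 0.20 × 0.80 / 0.03² ≈ 683, against a stated 690. Then 690 + 35 = 725, as stated. For 20% on placebo (175) against 1% on acoziborole (525), two-sided 5%, power is above 99.99%, in line with Protocol 10.1.2. The arithmetic is sound. The issue is what the endpoint measures.

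**2. What bears on location, and what enters the definition.**

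| Information | Where | Bears on location? | In the primary definition? |
|---|---|---|---|
| Skin TgSGP-PCR | Protocol 8.4, 10.8 | No: extracted nucleic acids, no step separating blood from tissue | Yes, alone |
| Entry microscopy | Protocol 4.1 | Partly: low sensitivity acknowledged in 1.6 | Eligibility only |
| Blood TBR, 18S, TgSGP-PCR | Protocol 8.4 | Indirectly: shows whether blood could be the source | No |
| IHC on the second punch | Protocol 8.4, 15.3 | Could, but no rule for scoring location | No, secondary |

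The first row is an inference from the extraction step; the documents do not discuss blood carry-over. The plan does allow for blood positives at baseline: the secondary analysis set admits subjects positive in blood or DBS (Protocol 10.2, SAP 3.4.3).

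**3. Where the plan brings skin and blood together.**
- Protocol 10.8 (Properties of diagnostic tests) and SAP 5.3.6 take skin TgSGP-PCR as a reference and assess the novel assays, including in blood, at enrolment. The relative sensitivity of a blood assay against that reference is the share of skin positives who are also blood positive, so its complement is the skin-positive, blood-negative share. This is a within-subject skin-by-blood table, but not for the conventional PCRs, not at Month 4, and not converted into a prevalence.
- SAP 5.3.2 repeats the analysis for each sample type separately, not jointly within subject.
- The last secondary endpoint in Protocol 2.2.3 compares all methods, alone or combined. It permits the table but does not specify it.

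**4. Size.** Let f be the share of skin positives that are positive only because of blood in the punch. The documents give no value, so f is an assumption. At 20% skin positivity, dermal prevalence is 0.20(1 − f) and the overstatement is 0.20f.

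| f (assumed) | Dermal prevalence | Overstatement |
|---|---|---|
| 5% | 19% | 1 point |
| 10% | 18% | 2 points |
| 15% | 17% | 3 points, the planned half-width |
| 25% | 15% | 5 points |
| 50% | 10% | 10 points |

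The table converts f to points. It does not estimate f.

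**5. Power.** Suppose only the remaining positives count, the 95% effect holds, and the arms stay at 175 and 525. Power is 99.8% at f = 50%, 94.9% at f = 75% and 71.5% at f = 90%. Excluding blood-positive subjects would also shrink the arms somewhat, so these figures are slightly optimistic. Power is not the difficulty.

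**The case against.** The strongest reply is that the effect may be negligible. A 2 mm punch has a cross-section of π × 1² ≈ 3.14 mm². At an assumed depth of 2 to 5 mm its volume is about 6 to 16 µL, and blood is only part of that. One DBS holds 50 µL (250 µL in five, Protocol 8.1.1) and the fresh sample is 3 mL. Parasites too scarce for microscopy, with the buffy-coat method preferred (Protocol 8.3.2), would often be absent from a few microlitres. This stands: f may be small, and no particular number of points should be attributed to the plan.

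The plan also has partial safeguards. IHC with at least two stains is planned for all sub-study subjects. The effectiveness objective depends on methods with better validity than TgSGP-PCR (Protocol 2.1.3). SAP 5.3.1 drops the word extravascular from the analysed endpoint. These soften the concern, but none enters the primary definition.

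Blood positivity does not exclude tissue parasites either. Restricting carriage to blood-negative subjects removes people who have both, so that figure is a lower one and not a corrected prevalence.

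Three stronger readings are tempting and not supported:
- A reader might infer that the plan never crosses skin with blood results. It does, for the novel assays at enrolment.
- A reader might infer that the 2% interim rule is distorted. That rule counts positivity in any sample (Protocol 10.9, SAP 2.5), so a blood-positive subject generally counts already. Only the efficacy condition tied to skin or dermis (Protocol 1.6, 2.1.3) could be touched.
- A reader might want the Month 4 comparison repeated in subjects who are skin positive and blood negative at Month 4. That conditions on a result treatment can change: clearing blood but not skin would move treated subjects into that class and add events to the active arm.

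**Conclusion.** The concern holds as a matter of definition and interpretation. Followed as written, the plan attaches an extravascular location to a result that cannot show it, and leaves the paired conventional blood PCRs out of the definition. This rests on one inference, that extraction from the punch loses location, and on the absence of any described step to separate blood.

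The size is unknown and may be small. The overstatement would reach the planned 3-point precision only if about 15% of skin positives came from blood alone, and the documents support neither that share nor any other. The sample-size and power figures reproduce. The sub-study is exploratory and the main safety conclusion is unaffected.

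**What to change.** - In Protocol 2.2.3 and 10.8 and SAP 5.3.1, name the endpoint *skin TgSGP-PCR positive*, and align SAP 1.2.2.
- At baseline, cross-tabulate skin TgSGP-PCR with the paired fresh-blood PCRs (TBR, 18S, TgSGP). Because TgSGP-PCR is run only after a positive TBR or 18S, samples negative on both count as blood negative. Show missing blood results as a separate row.
- Give prevalence with 95% CI twice: for all skin positives (an upper bound for dermal carriage detectable by this test) and for skin positive with blood negative (a conservative lower figure). Report IHC location as supporting evidence where available.
- Keep the Month 4 comparison on all sub-study subjects. Add a sensitivity analysis stratified by, or restricted to, baseline blood-PCR-negative status. Do not classify by Month 4 blood status.

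No new sample or assay is needed. The cost is SAP wording, one extra table, one sensitivity analysis and a less specific headline label.

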#### Secondary exploratory endpoints:

- Clinical parameters: occurrence of dermatitis and/or pruritus at baseline and M4.
- Diagnostic parameters: occurrence of IHC+, TBR- PCR+ and/or 18S-PCR+ in skin and blood at baseline and M4.
- Novel diagnostic parameters: occurrence of positive results by multiplex qPCRs, multiplex RT-qPCRs and SHERLOCK in blood and skin at baseline and M4.

- Occurrence of dermatitis, pruritus, IHC+, multiplex qPCRs+, multiplex RT-qPCRs+ and SHERLOCK+ in skin and blood at baseline and at M4.
- Occurrence comparisons between all diagnostic methods alone or in combination.

## 3. Study design and study design rationale

#### 3.1. Study design

This is a randomised, multicentre, double-blind, placebo-controlled, parallel-arm phase II/III study to assess the safety and tolerability of a single dose of acoziborole compared with placebo in adolescent and adult subjects seropositive to human African trypanosomiasis due to *T.b. gambiense* (g-HAT positive; not confirmed parasitologically [no demonstration of the parasite in any body fluid via microscopy]) in DRC and Guinea.

The double-blind, placebo-controlled nature of the study design will aid with minimising bias with the parallel-arm design allowing between subject comparison.

Subjects will be hospitalised at least 1 day before study treatment commences and will be randomised in a 3:1 ratio to acoziborole or matched placebo on Day 1 of the study. Following hospitalisation, subjects will attend follow-up visits at the study centre at 1- and 4-months post-treatment. At months 2 and 3, investigator contacts will be established between the site and subjects to ensure close follow-up of subjects and encourage study adherence. An on-site unscheduled visit will be proposed if deemed necessary by the investigator. Any subject with a positive parasitological test result during the study will end their participation in the study and be referred to the NSSCP for appropriate standard treatment.

In addition, a sub-study 'TrypSkin' to assess the presence of extravascular dermal *T.b. gambiense* in this population, will be proposed to subjects having given their consent to participate in the seropositive safety main study (in clinical sites participating in the sub-study only). Subjects can decide whether to participate or not in the sub-study independently of his/her participation in the main safety study.

#### 3.2. Study duration and duration of subject participation

The duration of the enrolment period is estimated to last for approximately 12 months. The study duration for each subject will be 4 months with the EoS visit occurring at 4 months post-treatment (with a window of -10 days to +1 month).

#### 3.3. Rationale of study design

The WHO-HAT elimination network recommended that the current study should include a sufficiently large number of subjects treated with acoziborole to reach a 95% probability to detect at least one uncommon AE. According to the sample size calculation, if 900 subjects are exposed to acoziborole, there would be a high chance (>99%) of detecting at least one AE (if the incidence rate is 1%). Therefore, it is planned that 900 subjects will be administered with acoziborole and 300 subjects with placebo, for an overall sample size of 1200 subjects.

[figure not shown]
To avoid any bias in AE/ TEAE collection, the study will be double-blinded and placebocontrolled with an allocation ratio of 3:1 (acoziborole:placebo). For more details about the rationale for the ratio decision, please refer to Section 10.1.2.

Standard safety assessments during this study will be the collection of TEAEs/AEs and laboratory safety parameters.

As the pivotal study (DNDi-OXA-02-HAT) demonstrated that 97.7% of TEAEs related to acoziborole occurred within 5 days after acoziborole administration, subjects will be hospitalised for an observational follow-up period of 5 days and will be asked to come back for on-site follow-up visits at Months 1 and 4. The visit at Month 4 corresponds to clearance of acoziborole as shown by results from the mass balance study (DNDi-OXA-03-HAT study).

Moreover, to ensure a close follow-up of subjects and encourage study adherence, investigator contacts will be established between the site and study subjects at Months 2 and 3. If deemed

necessary by the investigator, an on-site unscheduled visit will be proposed. The overall study design is summarised in Figure 2.

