# 10.1. Sample size and ratio determination

## 10.1.1. Sample size determination

The sample size was determined based on statistical probabilities to detect uncommon TEAEs in the active treatment (acoziborole) group (see Table 5). The definition for an uncommon event is a relative frequency between 0.1% and 1%. The median relative frequency is therefore 5/1000 (0.5%). The probability to detect at least 1 event if the true incidence rate is 0.5% is as high as 98% with 900 subjects and the probability is 83.5% for a true incidence rate of 2/1000 (0.2%). According to the calculations, 900 subjects exposed to acoziborole shows a high probability (>99%) of detecting at least one event (if the incidence rate is 1%) with a similar probability when exposing 1200 subjects. Therefore, 900 subjects will be administered with acoziborole and 300 subjects with placebo, for an overall sample size of 1200 subjects.

Table 5. Statistical probabilities for detecting uncommon treatment-emergent adverse
events (TEAEs) in the acoziborole group

Objectives/sample size (safety)	N=900	N=1200
Chance of detecting at least one event if the incidence rate is 1%	99.9%	99.99%
Chance of detecting at least one event if the incidence rate is 0.1%	59.36%	68.89%
Precision: 95% exact CI if one event is observed	0.003-0.6%	0.002-0.46%
Precision: 95% exact CI if three events are observed	0.068-0.97%	0.052-0.73%

CI=confidence interval; TEAEs=treatment-emergent adverse events.

Uncommon TEAEs are those with frequency  $\geq 1/1000$  and < 1/100 as per regulatory guidelines.

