## 10.1.2. Ratio determination

Operational properties of various allocation ratios for the following assumptions are as follows:

- 1. Total sample size (for safety main study): n=1200 (900 acoziborole and 300 placebo)
- 2. Excess rate (ER) for safety: 1% (acoziborole = 2% of AEs of interest, Placebo = 1%)
- 3. Probability to detect an infrequent AE ( $\leq 1\%$  upper limit of class)
- 4. Probability to detect an infrequent AE (0.5% mid-class)

5. Total sample size for efficacy (TrypSkin exploratory sub-study): n=725 in order to ensure a minimum of 700 evaluable biopsies

6. Binary endpoint for efficacy: success=no tryps detected in punch skin at month 4, failure = at least one tryp-positive result in punch skin at Month 4

7. Probability to detect at least one trypanosome in derma at baseline: 20%

8. No effect of placebo on occurrence of tryps in derma at month 4: failure rate at 4 months=20%

9. Effect of 95% of acoziborole on occurrence of tryps in derma at Month 4 (efficacy): failure rate at Month 4 =  $0.05 \times 0.20 = 0.01$  or 1%

10. Excess rate of success in acoziborole group: 19% (assuming the same efficacy as stage 2 patients)

	Safety			Efficacy (for TrypSkin sub-study)		
Allocation ratio	Sample size for safety	Exact 95% CI limits of ER	Probability to detect an infrequent AE if occurrence rate = 1% (upper limit), = 0.5% (mid-class) and = 0.1% (lower limit of class)	Sample size for efficacy	Exact 95% CI limits of ER Estimate = 20%	Power (chance to detect a difference vs PBO) if acoziborole efficacy is 95%
3:1	PBO = 300 ACO = 900	Lower = -0.92% Upper = +2.41%	Upper: 99.99% Mid: 99.90% Lower: 59.36%	PBO = 175 ACO = 525	Lower = 13.38% Upper = 25.55%	99.99%
2:1	PBO = 400 ACO = 800	Lower = -0.64 Upper = +2.42%	Upper: 99.96% Mid: 98.18% Lower: 55.06%	PBO = 233 ACO = 467	Lower =14.02% Upper = 24.62%	99.99%
3:2	PBO = 480 ACO = 720	Lower = -2.30%* Upper = +0.66%*	Upper: 99.93% Mid: 97.29% Lower: 51.34%	PBO = 280 ACO = 420	Lower = 14.51% Upper = 24.15%	99.99%
1:1	PBO = 600 ACO = 600	Lower = -0.44% Upper = +2.51%	Upper: 99.75% Mid: 95.06% Lower: 45.23%	PBO = 350 ACO = 350	Lower: 14.81% Upper: 23.48%	99.99%

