#### Conclusions:

- The four allocation ratios allow detection, with sufficient probability, of an infrequent AE with an exception for the lower limit of the class (0.1%) of infrequent events. In that case, the larger the sample in the acoziborole group, the better the probability of detection.
- The upper limit of the exact 95% CI of the ER of AEs is similar irrespective of the allocation ratio.
- The lower limit of the exact 95% CI is closer to the estimate (shorter 95% CI) with a balanced (1:1) allocation ratio.
- The power of a test of success rate (success = no trypanosome observed in skin punch sample at Month 4) is excellent irrespective of the allocation ratio if the effect of acoziborole is similar to the efficacy in stage 2 (efficacy ≥95%).
- The advantage of an allocation of 3:1 is to maximise the number of seropositive subjects exposed to acoziborole. There is a small disadvantage in the exact lower limit of the 95% CI (larger CI), but no real advantage in the power of the efficacy test.
- The main disadvantage of the balanced allocation ratio (1:1) is a smaller number of exposed subjects.

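### The 3:1 detection probability at 0.5% incidence is 98.90%, not the printed 99.90%; and if sufficient detection means 95%, 900 exposed subjects fall short below about 0.33%, not only at 0.1%

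*Protocol*

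**What the plan says.** Protocol 3.3 gives the sizing aim: "a sufficiently large number of subjects treated with acoziborole to reach a 95% probability to detect at least one uncommon AE". No incidence rate is attached to the 95%. The same paragraph supports 900 exposed with a probability above 99% at an incidence of 1%.

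Protocol 10.1.1 and SAP 2.4.1 define uncommon as 0.1% to 1% and take 0.5% as the middle of the class. They state: "The probability to detect at least 1 event if the true incidence rate is 0.5% is as high as 98% with 900 subjects". They then give 83.5% at 0.2%, and Table 5 (SAP Table 2.4.1.1) gives 59.36% at 0.1%. Table 5 also prints 68.89% at 0.1% for 1200 exposed. The resulting design is: "Therefore, 900 subjects will be administered with acoziborole and 300 subjects with placebo, for an overall sample size of 1200 subjects".

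Protocol Table 7 (SAP Table 2.4.3.1) compares four allocation ratios at 1%, 0.5% and 0.1%. The chosen 3:1 row reads, in per cent, "Upper: 99.99% Mid: 99.90% Lower: 59.36". The conclusions below the table say that the four ratios "allow detection, with sufficient probability, of an infrequent AE with an exception for the lower limit of the class (0.1%) of infrequent events". SAP 2.4.3 draws the same conclusion.

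**The concern.** The 99.90% conflicts with the 98% given for the same rate and the same 900 subjects. It sits in the row of the ratio that was chosen, in the table used to justify that choice.

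The conclusion that only the 0.1% limit falls short is hard to square with the 83.5% printed for 0.2%, if the standard is the 95% of Protocol 3.3. Detection of uncommon TEAEs is the stated basis for the sample size of a trial whose primary objective is safety. Readers will have to interpret adverse events that were not observed. Taken at its word, the conclusion suggests that nearly the whole class, down to 1 in 1,000, would have shown itself with the intended probability.

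**Working it through.** **Inputs.** Exposed to acoziborole: 900 (3:1), 800 (2:1), 720 (3:2), 600 (1:1), from Protocol Table 7. Class limits 0.1% to 1% and mid-class rate 0.5%, from Protocol 10.1.1. Target 95%, from Protocol 3.3.

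**Formulas.** The probability of at least one event is P = 1 − (1 − p)^n. The lowest incidence detected with 95% probability is p = 1 − 0.05^(1/n). The number needed for 95% is n = ln(0.05)/ln(1 − p).

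**The plan's own figures, n = 900**

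| True incidence | Recomputed | Printed |
|---|---|---|
| 1% | 1 − 0.99^900 = 99.99% | >99% (text), 99.9% (Table 5), 99.99% (Table 7) |
| 0.5% | 1 − 0.995^900 = 98.90% | 98% (text), **99.90%** (Table 7) |
| 0.3% | 1 − 0.997^900 = 93.31% | not given |
| 0.2% | 1 − 0.998^900 = 83.50% | 83.5% |
| 0.1% | 1 − 0.999^900 = 59.36% | 59.36% |

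All but one printed figure reproduce, allowing for rounding or truncation.

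**The 0.5% cell.** The Poisson form, 1 − exp(−4.5), gives 98.89%, so the choice of formula does not explain 99.90%. That value would need ln(0.001)/ln(0.995) = 1378.1, or 1,379 exposed. The other three mid-class cells reproduce to about 0.01 point: 98.19% for 800 (printed 98.18%), 97.29% for 720 and 95.06% for 600. A digit error for 98.90%, carried into the SAP, is the likely cause.

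**The n = 1200 cell.** 1 − 0.999^1200 = 69.90% (Poisson 69.88%), against 68.89% printed in Table 5 and SAP Table 2.4.1.1.

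**Where 95% is reached**

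| Ratio | Exposed | Lowest incidence with 95% detection |
|---|---|---|
| 3:1 | 900 | 0.332% |
| 2:1 | 800 | 0.374% |
| 3:2 | 720 | 0.415% |
| 1:1 | 600 | 0.498% |

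For 3:1, exactly 0.33% gives 94.9%, 0.333% gives 95.03% and 1 in 300 gives 95.05%, so 1 in 300 is the safe round statement. The range from 0.1% to 0.332% is (0.332 − 0.1)/(1 − 0.1) = 26% of the class on a linear scale and log10(3.32) = 52% on a log scale. For 95% detection at 0.3%, 0.2% and 0.1%, the numbers exposed would be 998, 1,497 and 2,995.

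**Events not seen.** With 0 of 900, the exact two-sided 95% upper limit is 1 − 0.025^(1/900) = 0.41%. The Wilson limit is 1.96²/(900 + 1.96²) = 3.84/903.84 = 0.43%. The 0.332% above equals the one-sided 95% limit, which is not the interval specified in SAP 3.1.

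**The case against.** The strongest defence is that the conclusion is true at every rate Table 7 evaluates. At 1% and 0.5% all four ratios reach 95% (the lowest value at 0.5% is 95.06%, for 1:1), and at 0.1% none does. Sufficient probability is not defined where it is used, so reading it as 95% is an inference, although 95% is the only numeric standard given for detection. The decline below 0.5% is disclosed: 83.5% and 59.36% are both printed. All of this stands. The sentence is imprecise between the tabulated rates rather than false at them.

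A reader might infer that 900 subjects fail the recommendation in Protocol 3.3, or that the trial is too small. The documents do not support that. The recommendation names no rate, and at the plan's own mid-class rate 900 exposed give 98.90%. Nor is adequacy argued only at 1%. Protocol 3.3 alone does so, but 10.1.1 and SAP 2.4.1 add 0.5% and 0.2%. Whether 1% lies inside the class is itself unsettled: the Table 5 footnote excludes it, while Table 7 treats it as the upper limit.

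A reader might also infer a failure against the target product profile in Protocol Appendix 1. The requirement for studies that detect events from 1/100 to 1/1,000 belongs to its scenario 3, treatment of suspects without parasitological examination. It sets no detection probability, and this trial enrols subjects who have had that examination.

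None of these points explains the 99.90%, or reconciles an exception confined to 0.1% with 83.5% at 0.2% on a 95% standard.

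**Conclusion.** Two printed probabilities are wrong in both documents, each by about one percentage point: 99.90% should be 98.90% (too favourable to the chosen ratio) and 68.89% should be 69.90% (too low). These corrections rest only on the binomial formula, which reproduces the neighbouring figures.

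The conclusion on sufficiency is too favourable if sufficient means 95%. On that reading, 900 exposed fall short for every incidence from 0.1% to about 0.33%, roughly a quarter of the class on a linear scale and half on a log scale. This assumes 900 exposed, independent subjects and complete ascertainment of events.

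The design is unaffected: 98.90% still exceeds 95%, and 3:1 has the lowest 95% threshold of the four ratios. The point concerns how the design property is stated and how unseen events are later described. Neither document claims that an unseen event has been ruled out.

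**What to change.** 1. In Protocol Table 7 and SAP Table 2.4.3.1, change the 3:1 entry at 0.5% from 99.90% to 98.90%.
2. In Protocol Table 5 and SAP Table 2.4.1.1, change the entry for 1200 exposed at 0.1% from 68.89% to 69.90%.
3. In Protocol 3.3 and the conclusions of Protocol 10.1.2 and SAP 2.4.3, state the standard and the range. Suggested text: *At least 95% probability of observing one or more events is reached from a true incidence of about 0.33% (1 in 300) with 3:1, 0.37% with 2:1, 0.42% with 3:2 and 0.50% with 1:1, and is not reached below these rates; with 3:1 it is 93.3% at 0.3%, 83.5% at 0.2% and 59.4% at 0.1%.* The threshold must be given by ratio, because the sentence covers all four and 0.33% would be wrong for three of them.
4. For events not seen, report the upper limit of the two-sided 95% interval required by SAP 3.1, and name the method: about 0.41% (exact) for 0/900. Use the number actually exposed rather than a fixed 900, because SAP 3.4.2 and 3.4.4 analyse by actual treatment received after misallocation was found.

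The cost is wording in two documents and a slightly less favourable stated property. Sample size, allocation and conduct are unchanged.
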